1. STUDY DETAILS

1.1 Study objectives

1.1.1 Primary and secondary objective

Primary objective:	Endpoints:
To evaluate the efficacy of inhaled AZD8871 600 µg in patients with moderate to severe COPD	
Primary
 
• Change from baseline in Trough FEV₁ on Day 15. 
Secondary
 
• FEV₁ AUC_{(0-4)/4h} (area under the curve for the change in FEV₁ from baseline to 4h, normalised by the time window) at Day 1, Day 8, and Day 14.• FEV₁ AUC_{(0-8)/8h}, AUC_{(0-12)/12h}, and AUC_{(0-24)/24h} at Day 1 and Day 14.• Change from baseline in Trough FEV₁ on Day 2, and Day 8.• Change from baseline in Peak FEV₁ on Day 1, Day 8 and Day 14.• Change from baseline in Trough FEV₁ over treatment duration.• Change from baseline in Peak FEV₁ over treatment duration.• Change from baseline in Total Score of Breathlessness, Cough Sputum Scale (BCSS) questionnaire and cough, breathlessness and sputum individual domain scores from Day 1 to Day 8, from Day 9 to Day 14 and during the whole treatment duration.• Change from baseline in CAT from Day 1 to Day 8, from Day 9 to Day 14 and during the whole treatment duration.• Rescue medication use from Day 1 to Day 8 and from Day 9 to Day 14.

Secondary objective:

To investigate the PK of AZD8871 600 µg and its primary metabolite after multiple dose administration of inhaled AZD8871 in patients with moderate to severe COPD

Endpoints:

On serial PK sampling days, the following PK parameters will be calculated for AZD8871 and its primary metabolite LAS191861 when applicable:

- Day 1: Maximum plasma concentration (C_{max}), time to reach maximum plasma concentration (t_{max}), time to reach last quantifiable plasma concentration (t_{last}), area under the plasma concentration-curve from time 0 to the time of last quantifiable concentration (AUC_{last}), area under the plasma concentration-curve from time 0 to 24 hours post-dose $AUC_{(0-24)}$.
- Day 14: C_{max} , t_{max} , t_{last} , AUC_{last} , $AUC_{(0-24)}$, average plasma concentration during a dosing interval (C_{avg}), fluctuation index during a dosing interval (%Fluc), accumulation ratio for C_{max} [$Rac(C_{max})$] and accumulation ratio for $AUC_{(0-24)}$ [$Rac(AUC_{(0-24)})$].

Additional parameters may be determined where appropriate (e.g. metabolite to parent ratios).

1.1.2 Safety objectives

Safety objectives:

To evaluate the safety and tolerability of inhaled AZD8871 600 µg in patients with moderate to severe COPD

Endpoints:

- Adverse events (AEs)/Serious Adverse Events (SAEs).
- Vital signs.
- Electrocardiogram (ECG).
- Clinical laboratory assessments.

1.1.3 Exploratory objectives

Exploratory objectives:

To evaluate patient's response to inhaled AZD8871 600 µg in patients with moderate to severe COPD

Endpoints:

- COPD exacerbations.
- Cough VAS.
- Cough monitoring.
- CCI

1.2 Study design

This is a randomised, placebo-controlled, double-blind, 3-way complete crossover William's design, international, multi-centre Phase IIa multiple dose study of 1 dose level of AZD8871, an active comparator (Anoro[®] Ellipta[®]) and placebo using a DPI device once daily, for 2 weeks, in patients with moderate to severe COPD. This multi-centre study will be conducted at approximately 5 sites in Germany and United Kingdom (UK). It is planned that approximately 72 men and non-childbearing female aged 40 to 85 years (both inclusive) with moderate to severe COPD will be randomised in a 1:1:1:1:1:1 ratio to 1 of 6 treatment sequences. A subset of 36 patients, who will have specifically consented for pharmacokinetics (PK), will also undergo PK assessments. The study includes 12 visits and the entire study period is scheduled to take from a minimum of 6.5 months (182 days) to a maximum of 7.5 months (217 days) for each individual patient. The aim is to ensure at least 54 patients complete the study.

Screening period: This will last up to 28 days and consists of a Screening Visit (Visit 1 and Visit 2) and a run-in period.

Patients will be requested to stop their usual COPD therapy after signing the ICF at Visit 1 and will be maintained on a mono-component ICS therapy, if required. Patients that were taking any LAMA and/or LABA will be maintained with ipratropium (20 µg × 2 puffs 4 times per day) between Visit 1 and Visit 2. In addition, salbutamol 100 µg will be provided as rescue medication during the study as needed (rescue medication has to be discontinued 6 hours before any pulmonary function test). The study will consist of a Screening period, 3 treatment periods (each separated by a wash-out period), and a Follow-up Visit.

Visit 1 and Visit 2 could be performed on the same day if no wash-out of prior medication is required and the patient visits the site in fasting condition. In case any wash-out of prior medication is required, then Visit 2 will be performed after the wash-out is complete. All the screening assessments can be performed at Visit 1 or Visit 2, based on the site's preference, except for the following:

- ICF: This must be completed at Visit 1 before any study-specific assessments are performed
- Reversibility test with salbutamol and spirometry: This must be performed at Visit 2 due to wash-out requirements.

Only patients who fulfil FEV₁ predicted values (FEV₁ ≥40% and <80% from predicted normal value and FEV₁/forced vital capacity (FVC) ratio <70%) postsalbutamol at Visit 2, will be started on the run-in period to assess clinical stability.

If the FEV₁ predicted values is not met, pulmonary function tests may be repeated at the latest, up to Day-14.

The duration of run-in period will be between a minimum of 14 and a maximum of 28 days (from Visit 2 to Visit 3). During the run-in period, all patients will receive ipratropium 20 µg x 2 puffs 4 times per day (must be discontinued 8 hours before any pulmonary function test). A paper diary will be used to collect AEs and concomitant medications during run-in and wash-out periods.

Treatment periods: After the screening period, patients must fulfil all inclusion criteria and no exclusion criteria prior to being randomised at Visit 3. Eligibility results will be used from the Screening period for any assessments that cannot be completed within Visit 3 (eg, laboratory assessments).

The duration of each treatment period will be 14 days. During the treatment periods, patients will receive all 3 possible treatments, with every patient receiving placebo in one of the periods in addition to their ICS mono-component therapy, if any. In each period, patients will receive two devices to ensure the double blindness of the study. Patients will receive one of the 3 following possible treatments in any given period, in a randomised manner:

- AZD8871 600 µg once daily
- Anoro[®] Ellipta[®] (55µg UMEC/ 22 µg VI) once daily
- Placebo once daily

[figure not shown]
Each of the 3 treatment periods will last for 14 days and will include 2 overnight stays at the study site and one ambulatory visit at the study site.

Each 14-day treatment period (except the last one) will be followed by a wash-out period of 42 to 49 days, during which patients will receive ipratropium 20 µg x 2 puffs 4 times per day (must be discontinued 8 hours before any pulmonary function test), in addition to their usual ICS therapy, if any.

From treatment period 2 onwards, on Day 1 of a new treatment period, a FEV₁ stability test will be performed pre-dose. FEV₁ stability check will be based on the prebest- test review. At Visit 6 and 9 the mean of the predose- FEV₁ (mean of the 2 measured values) should be within (±)20% or (±)200 mL compared to the predose- FEV₁ (mean of the 2 measured values) of the first treatment period (Visit 3). If the FEV₁ stability criterion is not met, an additional measurement could be taken within 30 min of the second predose- measurement, and the mean of the last 2 measurements will be considered for the FEV₁ stability criterion. If the FEV₁ stability criterion is still not met, the test can be rescheduled as soon as possible (up to a maximum of 3 times), and if the FEV₁ stability criterion is not met after re-testing, the patient should be withdrawn.

There will be a Follow-up Visit scheduled to take place 42 up to 49 days after last administration of the IP.

Figure 1 Study flow chart

d=day; FU=follow-up; V=visit.

During treatment periods 1 to 3, each patient will randomly receive one of the 3 possible treatments (AZD8871 600 µg, Anoro[®] Ellipta[®] or placebo).

1.3 Number of patients

The study was powered to demonstrate superiority of AZD8871 600 µg versus Anoro[®] Ellipta[®] for the primary efficacy endpoint. With a total of 54 patients, there is 90% power to detect a difference between AZD8871 and Anoro[®] Ellipta[®] treatments for the change from baseline to Trough FEV1 at Day 15 equal to 100 mL, assuming a SD of 220 mL, 2-sided 5% significance level and a normal distribution. Assuming an approximate 25% dropout, the total sample size required is 72 (multiple of 6 sequences). From previous studies, the screening failure rate is estimated to be approximately 50%; therefore approximately 145 screened patients will be required to achieve the goal of approximately 72 randomised patients.

No adjustment of the Type I error for multiple comparisons will be made in the study due to the exploratory nature of the study.

2. ANALYSIS SETS

2.1 Definition of analysis sets

2.1.1 Full analysis set

The Full Analysis Set (FAS) is defined as all patients randomised and receiving IP, irrespective of their protocol adherence and continued participation in the study. Patients will be assigned according to their randomised treatment, irrespective of whether or not they have prematurely discontinued. Patients who withdraw consent to participate in the study are included up to the date of their study termination. All efficacy analyses are based on the FAS and analysed according to the intent to treat principle.

2.1.2 Safety analysis set

The Safety Analysis Set (SS) consists of all randomised patients who receive at least one dose of IP. For summaries based on the SS, patients are included for a treatment only if they received at least one dose of that treatment (e.g. a patient who discontinues prior to taking the study treatment for period 2 will not be included in the safety set for that treatment).

The SS will be used for all summaries of safety data, and patients will be analysed according to the randomised treatment assignment for a given study period. Any important deviations from the randomised treatment assignment and any patients who received IP without being randomised for a given study period will be listed and considered when interpreting the safety data. Relevant safety summaries presented by actual treatment received will be considered if there are a considerable number of patients receiving another treatment than the one they were randomised to.

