9.3 Populations for analyses

For purposes of analysis, the following populations are defined:

Population	Description
Full Analysis Set (FAS)	
The FAS population is defined as all patients randomised and receiving IP, irrespective of their protocol adherence and continued participation in the study. Patients will be assigned according to their randomised treatment, irrespective of whether or not they have prematurely discontinued. Patients who withdraw consent to participate in the study will be included up to the date of their study termination. All efficacy analyses will be based on the FAS population and analysed according to the intent to treat principle.

Pharmacokinetic (PK)	
The PK population is defined as all randomised patients participating in the subset of PK patients, who took at least 1 dose of IP and have at least 1 of the parameters, C_{max}, AUC or AUC_{last} evaluable and are assumed not to be affected by factors such as protocol deviations (eg, disallowed medication, or incorrect IP received). All protocol deviations that occur during the study will be considered for their severity/impact and will be taken into consideration when patients are assigned to the PK population.
 
The exclusion of any patients or time points from the calculation of the PK parameters will be documented by the PK scientist including the reason(s) for exclusion. The available concentration data and PK parameter data for any patients excluded from the PK population will be listed only, and presented in the individual figures of concentration-time plots.

Per-Protocol (PP)	
The PP population is defined as a subset of FAS population constituted by those patients who did not present important deviations of the protocol that may affect efficacy (eg, met all inclusion/exclusion criteria liable to affect the efficacy assessment).

Safety Population	
The safety population consists of all randomised patients who received at least 1 dose of IP. Patients will be analysed according to the randomised treatment assignment in each period. Any important deviations from the randomised treatment assignment will be listed and considered when interpreting the safety data.

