42	Participation in another clinical study with investigational drug or device within the last 30 days or 5 half-lives (whichever is longer) prior to Screening.	Yes ⁺⁺⁺	No	Yes ⁺⁺⁺	No
43	Patient with known human immunodeficiency virus (HIV) infection or chronic hepatitis B or C infection.	Yes	No	No	No
44	Patient did not fulfill fasting requirements on Day 1, 8, and 14 before IP administration and following dose administration.	Yes ⁺⁺	No	No	No
45	Salbutamol not withheld at least 6 hours prior to any spirometry test for the study.	Yes	No	No	No
46	Ipratropium not withheld at least 8 hours before visits 3, 6, and 9 and during all treatment periods.	Yes	No	No	No
47	Patient could not abstain from list in protocol section 5.3	Yes	No	No	No
48	Patient who had 2 or more exacerbations of COPD within the last year prior to Screening	Yes	No	No	No
49	Patient unable to abstain from protocol-defined prohibited medications during the study, in the opinion of the investigator.	Yes ⁺⁺	No	Yes ⁺⁺	No
50	Patient is screening failure, but received study drug.	Yes	Yes	Yes	Yes
51	Incorrect study medication received.	Yes ⁺⁺	No	Yes ⁺⁺	No

Item #	Event description	Excluded from analysis set			
		P-PS	SS	PKS	FAS
52	Incorrect dose of study medication received.	Yes ⁺⁺	No	Yes ⁺⁺	No
53	Patient did not take any IP	Yes ⁺⁺	Yes	Yes ⁺⁺	Yes ⁺⁺
54	IP not taken at the study site at 9:00 AM±2 hours on Day 1 (Visits 3, 6 and 9).	Yes ⁺⁺	No	Yes ⁺⁺⁺	No
55	IP not taken within ±1 hours of dosing time of Day 1 and between 7 AM and 11AM on subsequent days of each treatment period.	Yes ⁺⁺	No	Yes ⁺⁺⁺	No
56	Patient has taken any of the restricted medications on a different regimen than the described in the protocol (Table 5, section 6.5).	Yes ⁺⁺	No	Yes ⁺⁺⁺	No
57	Procedure not performed (missing PK samples to prevent calculation of PK parameters).	No	No	Yes ⁺⁺	No
58	Study assessments (For example cough monitoring, spirometry, CC1 i-Stat, 12 Lead ECG and/or vital signs) are not performed at the scheduled timepoints.	No	No	No	No
59	Missing baseline data for the spirometry (FEV1 main variable)	Yes ⁺⁺	No	No	No
60	FEV1 and FVC measurements performed outside tolerance window	No	No	No	No
61	Fulfilling withdrawal criteria during the study but not withdrawn.	Yes	No	No	No
62	Fatal or life-threatening AE was not reported to the appropriate AstraZeneca representatives within 1 calendar day of initial receipt.	No	No	No	No

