3.5 Safety variables

3.5.1 Adverse events

AEs: The number and percentage of patients who experienced 1 or more treatment-emergent adverse event (TEAE), and the number of TEAE occurrences will be tabulated by treatment group. An AE is considered TEAE if the event occurs after first dose of IMP up to 42 days after the administration of the last dose of IMP or was present prior to the date of the first dose of IP, but increased in intensity after IP administration. All events present before first IMP are considered non-TEAEs.

Adverse events occurring before administration of IP (ie, not treatment-emergent) and the number of occurrences will be reported in the same way as TEAEs in a different Table.

A TEAE that occurs during a wash-out period will be associated to the last treatment taken. An AE that occurs more than 42 days after the last IP administration will not be counted as a TEAE.

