4.4 Safety

All safety summaries will be based on the SS. Any important deviations from the randomised treatment assignment will be listed and considered when interpreting the safety data.

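### Safety tables follow the randomised treatment of each period, so by default an event after a wrong kit is counted under a drug the patient did not take in that period

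*SAP*

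**What the plan says.** Attribution is by randomised treatment in both documents. SAP 2.1.2, second paragraph: "patients will be analysed according to the randomised treatment assignment for a given study period". Protocol 9.3: "Patients will be analysed according to the randomised treatment assignment in each period". SAP 4.4 bases every safety summary on this set.

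The first paragraph of SAP 2.1.2 decides who counts for a treatment: "patients are included for a treatment only if they received at least one dose of that treatment". Its example is discontinuation: "a patient who discontinues prior to taking the study treatment for period 2 will not be included in the safety set for that treatment".

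The plan foresees wrong-drug cases. SAP 2.2 names receipt of the wrong study drug as an important deviation. Item 51 of SAP Table 1 ("Incorrect study medication received") removes the affected timepoint or period from the per-protocol and PK sets but keeps the patient in the Safety Set.

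There are two safeguards:
- SAP 4.4: "Any important deviations from the randomised treatment assignment will be listed and considered when interpreting the safety data".
- SAP 2.1.2: "Relevant safety summaries presented by actual treatment received will be considered if there are a considerable number of patients receiving another treatment". No number is attached.

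For events between periods, SAP 3.5.1 uses different language: "A TEAE that occurs during a wash-out period will be associated to the last treatment taken". Protocol 9.4.2 has the same rule.

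**The concern.** Randomised attribution suits the FAS, where the intent-to-treat principle is wanted. Safety summaries describe what happened under exposure, so the natural label is the drug inhaled. Under the plan's default, a reaction to a wrongly supplied drug enters the column of the drug that should have been supplied. This applies to the TEAE tables, the heart rate and QTcF models, the counts of potentially clinically significant ECG values, and i-STAT potassium and glucose.

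The effect on means would be small. Low-count tables are where one or two patients can change what the reader sees. Two features make clean attribution worth having here: Protocol 2.3 says the heart rate effect needs further exploration, and Appendix A 5 provides for no data monitoring committee.

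The wash-out rule adds an inconsistency. After one wrong kit, an event on Day 14 would go to the randomised drug. The same event a few days later would, on the literal wording, go to the drug taken.

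**Working it through.** **Inputs.** Six sequences, three periods, each treatment assigned once per patient (Protocol 6.3, Table 4). 72 randomised, 54 expected completers, 25% dropout (Protocol 9.2). The documents give no wrong-kit rate and no number of patients per treatment in the safety tables; 54 to 72 per treatment is an assumed range.

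**The plan's own figure.** The paired-difference formula gives n = (220 × (1.960 + 1.282) / 100)² = 50.9, so 51 by the normal approximation and 53 by the t distribution. Power at 54 is 90.6% (t), against the stated 90%. 54 / (1 − 0.25) = 72. The design figure is reproduced, and nothing in this point changes it.

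**The two SAP 2.1.2 rules applied to wrong-treatment cases**, with the inclusion rule read literally:

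| Case | Attribution rule | Inclusion rule | Result |
|---|---|---|---|
| One whole period on the wrong treatment | Events go to the randomised column | Patient never received that treatment, so is not admitted to the column | Rules conflict |
| Wrong kit on some days only | Events go to the randomised column | Met | Misattribution only |
| Two period kits of one patient swapped | Events go to the randomised columns | Met, in the other period | Misattribution only |

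For the first case, the possible single errors number 6 sequences × 3 periods × 2 wrong treatments = 36. Each treatment is assigned only once, so replacing it in one period means the patient never receives it. The literal conflict therefore arises in 36 of 36: the patient leaves the denominator while the events are directed into that column.

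If the inclusion rule is instead read as requiring a dose in that period, as its example suggests, there is no conflict. The patient is counted and analysed under the randomised label, and misattribution remains.

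**Size of one misassigned event**, denominators held fixed:
- One column: 1/54 = 1.9 percentage points; 1/72 = 1.4.
- Difference between the two columns involved, if the event belongs in one and is counted in the other: 2/54 = 3.7; 2/72 = 2.8.
- The table of non-serious TEAEs at 5% or more (SAP 4.4.1.1) needs 0.05 × 54 = 2.7, so 3 patients, or 0.05 × 72 = 3.6, so 4 patients. Two of 54 is 3.7% and three is 5.6%; three of 72 is 4.2% and four is 5.6%. One event can move a term across the cut.

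**The case against.** The strongest reply is that protocol and SAP agree on a deliberate rule, in an exploratory Phase IIa study with mainly descriptive safety analyses, and that the SAP has an as-treated contingency. Kits are allocated by IVRS/IWRS (Protocol 6.3) and patient IDs are written on the kit, pouch and inhaler labels (Protocol 6.2), so errors may be very few or none. That is fair and limits the practical weight of the point.

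Three stronger readings are tempting, and the documents do not support them:

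- *The SAP flatly contradicts itself.* The two rules stand in separate paragraphs. The example shows that the inclusion rule was meant for dropout, and item 51 of Table 1 fits that reading. The conflict is one of literal wording, confined to errors covering a whole period.
- *A safety signal would be hidden.* Important deviations are listed, all AEs are listed, and patients with potentially clinically significant ECG values are listed with their sequence (SAP 4.4.1.1 and 4.4.1.3). Wrong-drug administration is reported as a medication error within 24 hours, IVRS/IWRS errors excepted (Protocol 8.4.4, Appendix B 8). An event would be misplaced in a table, not invisible. The direction is not fixed either, since errors can run between any two of the three treatments.
- *One dispensing slip spoils two periods.* Kits are dispensed separately on Day 1 of each period (Protocol Table 1), so a slip in one does not imply a second.

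What stands is that listing a deviation changes no count, percentage or model estimate. The as-treated tables have neither a threshold nor a commitment, and one or two patients might never be judged enough to trigger them.

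**Conclusion.** The point holds as a limited but real weakness. Followed as written, the plan labels wrong-kit safety data with a drug not taken in that period, and neither safeguard corrects the tables. The literal clash with the inclusion rule and the different wash-out wording leave the programmer to choose in some wrong-treatment cases.

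The size cannot be estimated from the documents, because they give no kit-error rate. With no errors, nothing changes. The 1.9 to 1.4 points per misassigned event rests on the assumed 54 to 72 patients per treatment and fixed denominators. Efficacy analyses and sample size are unaffected.

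**What to change.** In SAP 2.1.2 and Protocol 9.3, make the treatment actually received in each period the default for every Safety Set summary, and state that the same rule governs wash-out events. Keep randomised treatment for the FAS. Word the inclusion rule to match: a patient counts for a treatment if at least one dose of it was taken.

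Received treatment alone does not settle every case. Each period uses one SD3FL and one Ellipta inhaler, so a single wrong inhaler could give both actives, which has no column, and a mid-period kit error gives two treatments in one period. State in advance how such periods are classified, for example by listing them separately outside the three treatment columns. Keep the listing of deviations from randomised treatment.

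The cost is SAP and protocol wording, one extra classification rule and an actual-treatment variable. No new data collection should be needed, since the SAP's own as-treated contingency already presupposes that received treatment is known.
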